Hypothesis #1B: *Whole blood resuscitation will be associated with a lower incidence of 12 hour and 24 hour mortality, a lower incidence of death from exsanguination, incidence of MOF, nosocomial infection, improved transfusion ratios, lower overall blood transfusion requirements and shorter time to hemostasis as compared to those resuscitated with component therapy.*

Hypothesis #1C: *Whole blood resuscitation will be associated with an improved Glasgow Outcome Score-Extended at 6 months post injury as compared to those resuscitated with component therapy in patients with traumatic brain injury.*

Hypothesis #2A: *A nadir prehospital and acute phase resuscitation systolic blood pressure greater than or equal to 120 mmHg will be associated with improved traumatic brain injury outcomes at discharge and at 6 months.*

Linking Investigations in Trauma and Emergency Services

Task Order 2: Shock, Whole blood and Assessment of TBI (SWAT)

Hypothesis #2B: *The magnitude of the dose depth curve of systolic blood pressure during the prehospital and acute phase resuscitation will be associated with neurological outcome differences at discharge and at 6 months following traumatic brain injury.*

Research Design and Methods

Study Design: The LITES Network will perform a multicenter, prospective, observational cohort study over a 4 year period to determine the impact of whole blood resuscitation in trauma patients with hemorrhagic shock at risk of large volume resuscitation with and without TBI. Early whole blood resuscitation will be compared to standard component resuscitation. The study will also further characterize blood pressure and resuscitation endpoints in poly-trauma patients with traumatic brain injury. Six trauma sites with appropriate characteristics will be selected from network sites across the country. (Figure 2)

Figure 2

Study Setting: The study will be performed utilizing busy level I trauma centers from within the LITES Network located across the country, at sites where either whole blood has currently been incorporated into standard of care or where component blood transfusion is being utilized for patients in hemorrhagic shock at risk for large volume resuscitation. Due to the paucity of trauma centers who are currently utilizing whole blood for trauma patients as standard of care, the potential to incorporate additional sites may be required over time.

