Study Population: The study will focus on patients who suffer blunt or penetrating injury, transported to a Task Order 002 participating LITES trauma center with evidence of hemorrhagic shock at risk of large volume resuscitation.

Inclusion Criteria: Patients with blunt or penetrating injury who meet the following criteria: 1, 2, and 3

- 1) Has 2 or more of any of the following:
 - a. Hypotension (systolic blood pressure \leq 90 mmHg) in the prehospital setting or within 60 minutes of hospital arrival,
 - b. Penetrating mechanism,
 - c. FAST abdominal ultrasound is positive or equivocal or deferred by clinical team due to emergent visit to Interventional Radiology or a need for emergent laparotomy, thoracotomy, or vascular exploration.

Linking Investigations in Trauma and Emergency Services

Task Order 2: Shock, Whole blood and Assessment of TBI (SWAT)

- d. Heart Rate \geq 120 in the prehospital setting or within 60 minutes of hospital arrival.

AND

- 2) Taken to the Operating Room (laparotomy, thoracotomy or vascular exploration) or Interventional Radiology within 60 minutes of arrival.

AND

- 3) Blood/blood component transfusion in prehospital setting, ED or OR within 60 minutes of arrival.

Exclusion Criteria:

- 1) Age < 15
- 2) CPR > 5 consecutive minutes without ROSC
- 3) Penetrating brain injury with brain matter exposed
- 4) ED death
- 5) Known pregnancy
- 6) Known Prisoners

Inclusion and exclusion criteria will be assessed based on available information at the time of enrollment. Although all reasonable efforts will be made by the prehospital crew to either directly witness or obtain documentation of qualifying vitals, due to the nature of the emergency pre-hospital setting, there may be occasions where the prehospital medical crew must rely on verbal report of inclusion criteria, including qualifying vitals, from the referring hospital or EMS agency. In these instances, if, after subsequent review of outside hospital and/or EMS agency documentation, it is determined that the subject did not meet inclusion criteria and/or met exclusion criteria, the subject will remain enrolled in the study based on the information available at the time the subject was enrolled in the study.

Recruitment and Consent

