- For Aim 1C, a nonparametric analysis of variance will be used to compare the distribution of the GOS-E between the two groups. An effect size of 0.17 could be detected.
- For aim 2A, a nonparametric analysis of variance will be used to compare the distribution of the GOS-E between the two groups. An effect size of 0.28 could be detected.
- For aim 2B, a nonparametric correlation coefficient will be used to assess the association between GOS-E and the area under the systolic blood pressure curve. For each, a 95% confidence interval with a width of 0.19 can be estimated.
- For all secondary analyses, the type I error rate was set to 0.05, with a two-sided alternative hypothesis, and 90% power. For the Aim 1, the sample size will be 1,190. For Aim 2, the sample size will be limited to those with a traumatic brain injury. For the purposes of this study, this is expected to be 35% or a total of 417 participants.

Analyses

AIM#1: The analysis will begin by describing the baseline demographic and clinical characteristics of the overall population and then stratified by whole blood usage. The characteristics will be

Linking Investigations in Trauma and Emergency Services

Task Order 2: Shock, Whole blood and Assessment of TBI (SWAT)

compared among those who receive and who do not receive whole blood. For discrete variables, proportions will be generated and a chi-square test will be used to test for differences between the proportions. For continuous characteristics, means (medians) and standard deviations (interquartile ranges) will be calculated and t-tests (Wilcoxon) will be used to compare the means (distributions) among those who receive and do not receive whole blood.

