A two-sided z-test for correlated proportions will be used to compare the distribution proportions of GOS-E at 6-months between those with a prehospital and acute phase resuscitation systolic blood pressure greater than or equal to 120 mmHg to those who do not. A hierarchical polytomous logistics regression model will be used to control for the within-institution clustering. The model will be used to assess the independent impact of whole blood after controlling for the clustering effect and the potential confounding effects of baseline characteristics. As was done in Aim#1A, the propensity for a prehospital and acute phase resuscitation systolic blood pressure greater than or equal to 120 mmHg will be generated using a boosted logistic regression model which will include all baseline characteristics, including site and whole blood usage. The same analytic approach will be used to measure outcomes at discharge except a hierarchical logistic regression model will be used.

Hypothesis#2B: The area under the curve of systolic blood pressure during the prehospital and acute phase resuscitation will be generated for each study participant. The analysis will begin by comparing the baseline characteristics with the area under the curve. For discrete variables, bivariate linear regression models will be generated (area under the curve as the dependent variable and the discrete baseline characteristic as the independent variable). For continuous characteristics, the correlation will be assessed.

Hierarchical models will be used to adjust for within-institution clustering. Hierarchical bivariate linear regression models will be used to assess the association of baseline characteristics associated with area under the curve. A stratified propensity analysis will be used to estimate the association of area under the curve with GOS-E at six months. A hierarchical linear regression

Linking Investigations in Trauma and Emergency Services

Task Order 2: Shock, Whole blood and Assessment of TBI (SWAT)

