model will be generated using the area under the curve as the dependent variable and the baseline characteristics as independent variables to generate an estimated area under the curve (propensity score) for each subject. The population will then be separated into five strata of equal sample size, based on the propensity. Within each stratum, the association of the area under the curve with outcome will be assessed using a hierarchical polytomous logistic regression model (outcome: GOS-E at six months, independent variable: area under the curve).

To determine the association across strata and if the association differs across strata, a multinomial polytomous regression model with GOS-E at six months as the outcome, area under the curve, an indicator of stratum, and the two-way interaction as independent variables will be fit.

The same analytic approach will be used to measure outcomes at discharge except a hierarchical logistic regression model will be used.

Subgroup Analysis: The general approach to assess the homogeneity of a treatment effect across subgroup will be to include an interaction term between the treatment variable and the characteristics defining the subgroup in the regression model. A statistically significant interaction term would indicate that the null hypothesis of a homogenous effect would be rejected indicating a differential effect of the treatment across the subgroups. For example, when examining the homogeneity of the effect of whole blood on the primary outcome among those with and without a traumatic brain injury, the hierarchical logistic model will be modified to include a main effect for traumatic brain injury and the two-way interaction between whole blood use and traumatic brain injury.

[figure not shown]

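### Hypothesis 2B is about the dose depth of systolic pressure, but its exposure is a plain area under the SBP curve with no reference level or time scaling

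*Combined protocol and SAP*

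**What the plan says.** Under Objectives/Specific Aims/Hypothesis, the exposure in Hypothesis #2B is "The magnitude of the dose depth curve of systolic blood pressure during the prehospital and acute phase resuscitation", to be related to neurological outcome at discharge and at 6 months. The term dose depth is not defined there or anywhere else.

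Under Analyses, Hypothesis#2B, the exposure becomes an area: "The area under the curve of systolic blood pressure during the prehospital and acute phase resuscitation will be generated for each study participant". A hierarchical linear regression with this area as dependent variable gives each patient a predicted area, and five equal-sized strata are formed on the prediction. The within-stratum model is specified as "outcome: GOS-E at six months, independent variable: area under the curve". The across-strata model adds only stratum and its interaction with area.

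The Power Analysis uses the same exposure for Aim 2B: "a nonparametric correlation coefficient will be used to assess the association between GOS-E and the area under the systolic blood pressure curve". Its precision statement is "For each, a 95% confidence interval with a width of 0.19 can be estimated". For the number with brain injury it says "this is expected to be 35% or a total of 417 participants".

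None of these places gives a reference pressure, a division by time, or an end to the acute phase. Two SBP levels do appear elsewhere: 90 mmHg in the Inclusion Criteria and 120 mmHg for nadir SBP in Hypothesis #2A.

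**The concern.** Depth is a distance from something, and a dose of depth is that distance accumulated over time. An unqualified area under an SBP curve is measured from zero. It adds every reading, high or low, and equals the patient's mean SBP times the time observed. This has two consequences.

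- Later high readings offset earlier low ones, so patients with quite different low-pressure histories can share a value.
- A patient watched for longer gets a larger value at the same pressure.

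The area is the response in the exposure model, the basis of the predicted values that define the strata, and the only exposure in the outcome models, so the choice runs through all of 2B. If outcome depends on how low pressure went and for how long, the association is diluted, and a null result could not be read as absence of a dose-depth effect. If observation time varies, an association could reflect length of transport or resuscitation instead of pressure.

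**Working it through.** **1. The plan's own figure.** Inputs from the Power Analysis: n = 417 (0.35 × 1,190 = 416.5) and 95% confidence. Width = tanh(atanh r + 1.96·SE) − tanh(atanh r − 1.96·SE), with SE = 1/√(n − 3) = 1/√414. This gives 0.192 at r = 0, 0.190 at r = 0.1 and 0.184 at r = 0.2. With the Spearman variance, SE = √(1.06/414), it gives 0.198, 0.196 and 0.190. The stated 0.19 is reproduced. By this formula the width depends only on n and r, so redefining the exposure does not alter it.

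**2. Offsetting, over the same 4 hours (assumed traces).**

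- Trace A, 110 mmHg throughout: area = 4 × 110 = 440 mmHg·h. Area below 90 = 0. Area below 120 = 4 × 10 = 40.
- Trace B, 65 mmHg for 1 h, then 125 mmHg for 3 h: area = 65 + 375 = 440 mmHg·h. Area below 90 = 25. Area below 120 = 55.

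The planned exposure is identical. The deficits differ at both reference levels.

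**3. No time scaling.** 70 mmHg for 4 h gives 280 mmHg·h; 120 mmHg for 2 h gives 240. The patient who is low throughout has the larger area. Per hour, the means are 70 v 120 mmHg and the deficits below 90 are 20 v 0 mmHg.

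**4. How good a proxy over a fixed window?** Assumed traces: 4 hours, readings every 10 minutes, mean 115 mmHg, between- and within-patient SD each 15 or 25 (four settings), autocorrelation 0.8, 60,000 traces per setting. Correlation of the area with the deficit:

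- below 90: Pearson -0.66 to -0.77, Spearman -0.85 to -0.93;
- below 120: Pearson about -0.92, Spearman -0.98 to -0.99.

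A different assumed shape (recovery from a nadir near 80 towards 120 mmHg, fixed 240 minutes) gives Spearman -0.63 below 90 and -0.93 below 110.

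**5. Varying observation time.** With the first set of traces cut at between 1 and 4 hours, the area correlates 0.80 to 0.91 with duration. With the recovery traces observed for 60 to 300 minutes, its rank correlation is 0.96 with duration and only -0.14 with the deficit below 90.

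**6. What dilution could cost over a fixed window.** Suppose outcome depends linearly on the deficit alone, with correlation 0.16 (an assumption). Power = Φ(atanh r × √414 − 1.96), about 91% at r = 0.16. Measured through the area, r is 0.16 × 0.66 = 0.106, 0.16 × 0.77 = 0.123 (reference 90) or 0.16 × 0.92 = 0.147 (reference 120). Power is then about 58%, 71% and 85%.

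**The case against.** The strongest reply is that the plan never says dose depth means distance below a reference. Hypothesis 2B does not mention hypotension. General Hypothesis #2 speaks only of differences in SBP, and the Background calls the best pressure in these patients poorly characterised and cites animal data in favour of permissive hypotension. An exposure without a threshold is defensible in that setting, and Hypothesis 2A already examines nadir SBP against 120 mmHg. The hypothesis is also secondary, in an observational cohort.

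Much of this stands. Part of the defect is a missing definition. The 90 mmHg level is an eligibility criterion that the plan never offers as an analytic cut-point. A reader might infer that the area says nothing about low pressure, or that a null 2B would be worthless. The documents do not support that: over a fixed window the area orders patients much as the deficit does, nearly perfectly so at 120 mmHg, and the correlation named in the Power Analysis is rank-based. The weaker Pearson figures at 90 mmHg largely reflect the skew and zeros of the deficit itself, though they do matter for outcome models that enter the area linearly.

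Two things survive. The word depth needs a reference level, and the plan gives none. Hypothesis 2A does not fill the gap, because a dichotomised nadir carries depth without duration. And nothing in the reply addresses the absence of time scaling.

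**Conclusion.** The point holds as a mismatch between hypothesis and exposure. As written, 2B relates GOS-E to mean SBP times observed duration, not to depth and duration of low pressure. That the area does not isolate the deficit, and that it grows with time observed, are matters of arithmetic and need no simulation.

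The size depends on assumptions. Over a common 4-hour window the area is an imperfect but informative proxy, close at 120 mmHg and looser at 90 mmHg. If observation time varies as much as assumed above, the area is mainly a measure of duration, and this is the larger problem. All SBP traces are illustrative; the documents give no SBP distribution or observation times. The primary outcome, the sample size and the stated 2B precision are unaffected. The matter should be settled before analysis, but it does not threaten the study.

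**What to change.** In Analyses, Hypothesis#2B, define the exposure as the area between a prespecified reference SBP and the curve, counted only while SBP is below the reference, divided by time observed. State when observed time starts and ends and how pressure is taken between readings. In the example above this gives 0 v 6.25 mmHg at reference 90 (25/4) and 10 v 13.75 mmHg at reference 120 (40/4 and 55/4), so the two traces are told apart.

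The study team should justify the reference as an analytic cut-point, not a treatment target. The protocol already contains 120 mmHg (Hypothesis 2A) and 90 mmHg (eligibility); one could be primary and the other a sensitivity analysis. Keep time-averaged SBP, in place of the unscaled area, as a companion exposure. Use the same parameter in the exposure model, the outcome models and the Aim 2B line of the Power Analysis.

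The data are the serial vitals already collected. The cost is more than wording, because the deficit is skewed with many zeros, especially at 90 mmHg (29 to 55% of the simulated 4-hour traces, which is not an estimate for this trial). The linear model for the exposure may need a two-part or transformed form. The five strata can stay, since they are formed on predicted values, which need not pile up at zero.

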Sample Tracking, Management and Storage: After sample obtainment, processing and storage, samples will initially be batched sent to the University of Pittsburgh biological sample repository where it will be tracked, managed and stored until the necessary translational or mechanistic measurement are performed. The CCC and DCC have a long track record of coordinating such processes.

Power Analysis: The prospective cohort study will utilize time to 4 hour mortality for its primary outcome to power the study. Based upon the 6 LITES Network sites admission history that will be utilized and their respective volume of hemorrhagic shock patients meeting inclusion and exclusion criteria and a 3.5 year enrollment time period, we plan to initiate sampling on 1,050 patients over the enrollment time period of the study. With an 85% consent rate which is an estimate based upon prior studies of similar nature, we will consent for participation 892 patients for the study. With an estimate baseline rate of 4 hour mortality of 11.1 % derived from the PROPPR study, there will be 90% power to detect a hazard ratio of 1.9.

Calculations are based on the primary aim of the study based on the following assumptions:

- Type I error rate of 0.05
- Two-sided alternative hypothesis

Linking Investigations in Trauma and Emergency Services

Task Order 2: Shock, Whole blood and Assessment of TBI (SWAT)

- 6 sites will be involved, three whole blood and three component sites
- Each site will enroll 175 participants in 3.5 years of enrollment, of which, 85% will be eligible for the study (149)
- The calculations are based on Cox proportional hazard model
- A 4 hour event rate in the control (non-whole blood) group of 0.111

The power calculations for these secondary aims are presented below. When reporting the results of the analyses, caution will need to be taken with respect to the interpretation of the findings since they are secondary in nature.

The secondary outcomes in Aim 1B include binary outcome, continuous outcomes, and time to event outcomes. For the binary outcomes, the odds ratio that can be detected is presented in Table 1. For the continuous outcome, the effect size that can be detected is 0.13. Finally, for the time to event outcomes, the hazard ratio that can be detected over a range of event rates in the control group is also presented in Table 1.

Event Rate	.1	.2	.3	.4	.5	.6
Odds Ratio	1.76	1.56	1.49	1.46	1.46	1.48
Hazard Rate	2.69	1.70	.37	.30	.27	.30

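### Hypothesis 2B adjusts for baseline confounding only through fifths of the predicted blood-pressure area, which leaves some confounding, mostly in the two end fifths; adding the continuous score is a cheap remedy

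*Combined protocol and SAP*

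**What the plan says.** Under Analyses, AIM#2, Hypothesis#2B, a hierarchical linear regression of the area on baseline characteristics gives every patient an estimated area, which serves as the propensity score. Then: "The population will then be separated into five strata of equal sample size, based on the propensity".

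Two outcome models follow. The within-stratum model is specified as "outcome: GOS-E at six months, independent variable: area under the curve". The pooled model, used to judge the association across strata and whether it differs between them, is fitted "with GOS-E at six months as the outcome, area under the curve, an indicator of stratum, and the two-way interaction". Discharge outcomes follow the same scheme with a logistic model. The estimated area does not reappear as a covariate, no baseline covariate is listed, and no check of balance within strata is described.

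By contrast, the models for Hypotheses 1A, 1B and 1C each include the propensity for whole blood as a main effect.

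On size and error rate, the Power Analysis section states: "For all secondary analyses, the type I error rate was set to 0.05, with a two-sided alternative hypothesis, and 90% power". For the TBI subset "this is expected to be 35% or a total of 417 participants", and for 2B "a 95% confidence interval with a width of 0.19 can be estimated".

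**The concern.** Area is a continuous exposure and the score is its own prediction from baseline. Patients in the same fifth still differ in predicted area, and that difference moves the observed area. If predicted area also relates to GOS-E (sicker patients having both lower pressure and worse outcome, for example), the area coefficient within a fifth still carries part of the baseline confounding. Stratum indicators remove differences between fifths, not differences inside them.

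The leftover bias runs towards the crude association, so it could be read as support for Hypothesis 2B. It is also uneven, being largest in the lowest and highest fifths. The planned comparison of the association across strata would therefore compare strata with different amounts of residual bias.

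**Working it through.** **Inputs from the documents (Power Analysis).** Two-sided alpha is 0.05. Aim 2 has 417 patients: 0.35 × 1,190 = 416.5, the base being "For the Aim 1, the sample size will be 1,190". The same section also says "we will consent for participation 892 patients for the study", and 0.35 × 892 = 312. Both sizes were used below; reconciling them is a separate matter.

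**Inputs assumed, because the documents give none.** R2 of area on baseline: 0.1 to 0.7. Strength of the score/GOS-E link: odds ratio 1.5 to 4 per SD of the score, or a correlation with latent GOS-E of 0.4 to 0.6 (0.2 for weak confounding). A normal score, an assumed 8-category GOS-E distribution, and no site effect.

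**Step 1: the plan's own figure.** Fisher z half-width: 1.96/√(417 − 3) = 0.0963. Around r = 0 the width is 2 × tanh(0.0963) = 0.192; at r = 0.1 it is 0.190. The stated 0.19 is reproduced. With 312 patients the width would be 0.22.

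**Step 2: score variance left inside fifths.** The cut-points of a standard normal are ±0.8416 and ±0.2533.
- End fifth: mean 1.3998, variance 1 + 0.8416 × 1.3998 − 1.3998² = 0.219.
- Second and fourth fifths: 0.028. Middle fifth: 0.021.
- Average: w = (2 × 0.219 + 2 × 0.028 + 0.021)/5 = 0.103.

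**Step 3: share of the crude slope that remains.** Scale area to variance 1, of which R2 comes from the score, and let GOS-E depend linearly on the score with slope β and not on area. The crude slope is β·R2. Within fifths it is β·w·R2/(w·R2 + 1 − R2). The ratio is w/(w·R2 + 1 − R2). Adding the continuous score multiplies the standard error of the area coefficient by √[(w·R2 + 1 − R2)/(1 − R2)].

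| Assumed R2 | Residual share of crude slope | SE increase from adding the score | Type I error, common-slope ordinal test, n = 417, OR 1.5 to 4 |
|---|---|---|---|
| 0.1 | 0.103/0.9103 = 11% | √(0.9103/0.9): 0.6% | 4-7% |
| 0.3 | 0.103/0.7309 = 14% | √(0.7309/0.7): 2.2% | 5-14% |
| 0.5 | 0.103/0.5515 = 19% | √(0.5515/0.5): 5.0% | 7-22% |
| 0.7 | 0.103/0.3721 = 28% | √(0.3721/0.3): 11.4% | 10-37% |

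By stratum, with the same formula and that stratum's variance: in an end fifth 0.219/(0.219 × 0.3 + 0.7) = 29% at R2 0.3 and 0.219/(0.219 × 0.5 + 0.5) = 36% at R2 0.5. In the middle three fifths it is 3-6%.

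**Step 4: type I error, simulated with no effect of area.** The last column of the table is a one-degree-of-freedom test with stratum indicators. Other tests over R2 0.3-0.7 and correlation 0.4-0.6, at n = 312 and 417, gave:
- rank-score test with a common slope: about 6-33%;
- nominal multinomial test of area without the interaction (7 df): about 5-16%;
- nominal multinomial test of area plus interaction (up to 35 df): 4-9%.

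An ordinal test of area plus interaction (5 df) gave 5-31% at n = 417. At R2 0.1 or correlation 0.2 the nominal tests stayed at 3-7%. The heterogeneity test rose only to 5-10%.

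**Step 5: after adding the continuous score alongside the fifths.** The residual coefficient was about 0. The false-positive rate was about 3-6% at n = 417, and 3.5-7.5% at n = 312 with only 600 runs per setting. The simulated rise in standard error was about 2.5% at R2 0.3 and 12% at R2 0.7, close to the formula.

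**The case against.** The plan chooses a stratified propensity analysis by name, and fifths avoid assuming how GOS-E depends on the score. The simulations make that dependence linear, which favours the continuous score. The pooled model as written is multinomial with an interaction, and if GOS-E is treated as nominal the inflation is small (4-9%). Hypothesis 2B is secondary, the Power Analysis section asks for caution with secondary findings, and 2B is sized by interval width rather than by a test.

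Much of this stands as a limit on size. It does not remove the mechanism. The variance left inside fifths does not depend on the outcome model, a spline kept alongside the fifths answers the point about functional form, and general caution does not correct a bias with a direction. The plan also sets alpha at 0.05 for all secondary analyses. Whether polytomous means nominal or ordinal is not settled in the text, so the larger ordinal figures cannot be ruled out.

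Three stronger readings are tempting and not supported:
- A reader might infer that the plan carries a known false-positive rate of up to a third. The documents give neither the R2 nor the confounding strength, and that figure belongs to a common-slope ordinal or rank test under strong confounding. Rates inside a single end fifth ran from 4% to 33% across tests and set-ups, so none is claimed.
- A reader might infer that the pooled model ignores clustering because its sentence omits the word hierarchical. The Hypothesis#2B text already says that hierarchical models will adjust for clustering within institutions.
- A reader might say that GOS-E is regressed on area alone throughout. That is true only of the within-stratum models; the pooled model also has stratum and interaction terms.

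**Conclusion.** The point holds as a modest, specific weakness. Adjustment in 2B rests on fifths alone, and about 10% of a normal score's variance escapes it, mostly in the end fifths. The remaining confounding is about 11-28% of the crude slope if R2 lies between 0.1 and 0.7. What this does to the error rate depends on the test and on confounding strength: almost nothing when confounding is weak, about 4-16% for nominal multinomial tests, and up to about 30-37% for a common-slope ordinal or rank test when confounding is strong. All these sizes rest on a normal score, a linear link and no site effect. The effect on the heterogeneity test is small. None of this invalidates Aim 2. The change is worth making because the score is already computed and the plan uses the propensity directly in 1A to 1C.

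**What to change.** In Hypothesis#2B, add the continuous estimated area, linear or as a spline, as a covariate in both the within-stratum and the pooled models, and apply the same rule to the discharge outcomes. Keep the five strata and the area-by-stratum interaction for the heterogeneity test. State in the same sentence whether GOS-E is modelled as nominal or ordinal, since the operating characteristics depend on it.

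The cost is a sentence of analysis wording, one model term (a few more with a spline), and a standard error for area that is larger by about 1-12% over the R2 range considered. No extra data are needed.
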